4. RISKS AND BENEFITS OF THE INVESTIGATIONAL DEVICE AND CLINICAL INVESTIGATION

The risks associated with use of the NovoTTF-200A are the same as those associated with use of the approved Optune System. Principally, the risks are electrical or mechanical failure leading to electrical shock or electromagnetic interference, as well as the risk that the treatment will not be effective in delaying tumor progression or causing regression. Additional risks include skin irritation, and skin breakdown or infection at electrode sites. Other risks include headaches, fatigue, falls, and muscle twitching. Technical failure is extremely unlikely due to stringent compliance with all standard design and manufacturing safety protocols. In addition, appropriate measures have been taken to minimize the risk to study subjects, including preclinical *in vitro* and *in vivo* testing to ensure safe operation of the device.

Approximately 25 patients will be enrolled in the proposed study and will receive Novo-TTFA treatment. Participants are considered enrolled after their eligibility is confirmed and the coordinating center sends the enrollment confirmation to the site. Considering the minimal toxicity and promising efficacy seen in the GBM studies, the number of patients exposed to this treatment in the proposed study and the risks associated with the alternative treatments for these patients, the company believes that the possible benefits of NovoTTF-200A treatment clearly exceed its potential risks.

5. OBJECTIVES AND HYPOTHESES OF THE CLINICAL INVESTIGATION

a) Purpose and Objectives

Purpose

To test the feasibility of prophylactic cranial TTF therapy in preventing brain metastases in ES-SCLC patients who have a partial or complete response of extracranial disease after at least 4 cycles of first line chemotherapy.

Primary Objective

To measure the feasibility and compliance of NovoTTF-200A as prophylactic cranial TTF therapy, determined by % of patients continuing TTF therapy until intracranial tumor progression, discontinuation due to DLT, or 6 months.

Secondary Objectives

1. To evaluate time to intracranial failure after NovoTTF-200A.
2. To evaluate overall survival after NovoTTF-200A.
3. To evaluate the rates of intracranial failure at 2, 4, 6, 8, 10, 12 months after NovoTTF-200A.
4. To evaluate intracranial failure free survival after NovoTTF-200A.
5. To evaluate the rate of decline in HVL-R free recall, delayed recall and delayed recognition, COWAT and TMT Parts A and B at 2, 4, 6, 8, 10, 12 months after NovoTTF-200A.
6. To evaluate time to neurocognitive failure after NovoTTF-200A.
7. To evaluate neurocognitive failure-free survival after NovoTTF-200A.
8. To evaluate Quality of Life using the EORTC QLQ C30 with BN20 addendum after NovoTTF-200A.
9. To assess adverse events, severity, and frequency associated with NovoTTF-200A using the CTCAE version 5.0.

b) Hypotheses

The hypothesis of this study is that NovoTTF-200A will reduce the risk of developing brain metastases for ES-SCLC patients.

c) Intended Performance of the Investigational Device

This prospective open label pilot study is designed to study the safety, tolerability and feasibility of NovoTTF-200A to the brain as prophylactic cranial therapy for ES-SCLC patients.

d) Risks and Anticipated Adverse Device Effects That are to be Assessed

See **Section 4** (Risks and Benefits of the Investigational Device and Clinical Investigation).

6. DESIGN OF THE CLINICAL INVESTIGATION

1. General

a) Description of the Type of Clinical Investigation to be Performed

This is a prospective, single-arm, open-label multicenter pilot study. All patients will undergo TTFs using the NovoTTF-200A System set to an output frequency of 200 kHz. Patients on the study may receive chest irradiation at the discretion of the treating physician. Moreover, should the patient develop progressive extracranial disease, then the patient may receive systemic therapy at the discretion of the treating physician. All oncology therapies will be recorded in the clinical trial record.

NovoTTF-200A will be discontinued in patients who develop intracranial failure while on therapy. All patients who develop intracranial failure may undergo WBRT or best supportive care at the discretion of the treating physician.

All study follow-up procedures should continue according to the study's protocol until death, or until one of the other criteria for removal from the study is met (see **Section 3.C** below).

b) Outcome Measures

Primary Outcome Measure:

Feasibility, as measured by tolerability of TTFs, will be recorded as percentage of patients continuing TTF therapy until intracranial tumor progression, discontinuation due to DLT, or continuation of therapy for at least 6 months.

Secondary Outcome Measures:

1. Time to intracranial failure, as measured from date of starting NovoTTF-200A to intracranial failure as a first event. Death prior to evidence of intracranial failure is treated as a competing risk and will be censored on the time to intracranial failure curves.
2. Overall survival, defined from the date of starting NovoTTF-200A to death, or censored at the date of last follow-up.
3. Rate of intracranial failure at 2, 4, 6, 8, 10, 12 months after starting NovoTTF-200A
4. Intracranial failure free survival, defined from the date of starting NovoTTF-200A to the first intracranial failure or death (whichever occurs first) or, otherwise, censored at the last MRI imaging assessment date on which the patient was reported alive without intracranial failure.
5. Rate of decline in cognitive function as measured by HVLT-R free recall, delayed recall, and delayed recognition; COWAT; and TMT Parts A and B at 2, 4, 6, 8, 10, 12 months follow-up.
6. Time to neurocognitive failure, as measured by cognitive decline on a battery of tests: HVLT-R free recall, delayed recall, and delayed recognition; COWAT; and TMT Parts A and B.
7. Neurocognitive failure-free survival, defined from the date of starting NovoTTF-200A to neurocognitive failure (as measured by HVLT-R free recall, delayed recall, and delayed recognition; COWAT; and TMT Parts A and B) or death (whichever occurs first), censored at the last neurocognitive assessment on which the patient was reported alive without neurocognitive failure.
8. Quality of Life using the EORTC QLQ C30 with BN20 addendum.
9. Toxicity during NovoTTF-200A treatment based on incidence and severity of treatment emergent adverse events as evaluated using the CTCAE version 5.0

c) Methods and Timing for Assessing, Recording, and Analyzing Variables.

See under Statistical Considerations (**Section 9**).

2. Investigational Device(s) and Comparator(s)

The investigational device and comparators are described as part of the study treatments below.

3. Subjects

Inclusion Criteria:

1. 22 years of age and older
2. Life expectancy of > 3 months
3. Histologically proven ES-SCLC (any T any N and any M stage) within 6 months prior to start of study treatment with the NovoTTF-200A, with a partial or complete response to at least four cycles of first-line chemotherapy
4. Karnofsky performance status (KPS) > 70 (see **Appendix A**)
5. Adequate hematological, hepatic and renal function, defined as: Neutrophil count > $1.5 \times 10^9/L$ and platelet count > $100 \times 10^9/L$; bilirubin < $1.5 \times ULN$; AST and/or ALT < $2.5 \times ULN$ or < $5 \times ULN$ if patient has documented liver metastases; and serum creatinine < $1.5 \times ULN$.

Exclusion Criteria:

1. Evidence of brain metastases on MRI of brain with and without contrast
2. History of other prior malignancy within the past 5 years except for superficial skin cancers
3. No severe comorbidities:
 - a. History of significant cardiovascular disease unless the disease is well controlled.

Significant cardiac disease includes second/third degree heart block; significant ischemic heart disease; poorly controlled hypertension; congestive heart failure of the New York Heart Association (NYHA) Class II or worse (slight limitation of physical activity; comfortable at rest, but ordinary activity results in fatigue, palpitation or dyspnea).

- b. History of arrhythmia that is symptomatic or requires treatment. Patients with atrial fibrillation or flutter controlled by medication are not excluded from participation in the trial.
 - c. History of cerebrovascular accident (CVA) within 6 months prior to start of study treatment
 - d. Active infection or serious underlying medical condition that would impair the ability of the patient to received protocol therapy.
 - e. History of any psychiatric condition that might impair patient's ability to understand or comply with the requirements of the study or to provide consent.
4. Active implantable electronic medical devices in the brain; a skull defect, a shunt, or bullet fragments
 5. Known allergies to medical adhesives or hydrogel
 6. Unable to operate the NovoTTF-200A device independently or with the help of a caregiver
 7. If a female, currently pregnant, breastfeeding, or unwilling to avoid pregnancy while on study treatment.
 8. Concurrent brain directed therapy (beyond NovoTTF-200A as per protocol)
 9. Prior clinical trial participation with brain directed therapy
 10. Concurrent treatment clinical trials

4. Criteria for Removal from Study Therapy

Criteria for removal from study therapy include:

1. Patient request – The patient may withdraw from the study at any time.
2. Lack of compliance – The Sponsor or investigator may remove a patient from the study for lack of compliance to the study protocol.
3. Intolerable toxicity - Patients may be removed from study treatment for intolerable adverse events attributable to the device. Any serious adverse event deemed life threatening by the treating physician that is definitely related to the study device will be cause for immediate cessation of treatment.
4. Intracranial failure – As defined in section 9(a) of the protocol
5. Death

5. Enrollment Plan

a) Start Date of Enrollment

Enrollment of the first patient is expected during the second quarter of 2017.-

b) Total Expected Duration of the Clinical Investigation

The study is expected to last for 36 months.

c) Expected Duration of Each Subject's Participation

Subject participation in the trial is anticipated to be 10-15 months.

d) Number of Subjects Required to be Included in the Clinical Investigation

A total of 25 patients will be accrued for this study at up to three institutions. Any patients deemed screen failures may be replaced with a new patient.

e) Estimated Time Needed to Select this Number (i.e., Enrollment Period).

It is assumed that the accrual will take place over 24 months.

Enrollment Procedures

Guidelines for VICC and Participating Institutions

Prior to enrollment, a copy of the IRB approval at the site will be requested and kept on file at the Vanderbilt-Ingram Cancer Center (VICC) Coordinating Center. Eligible participants will be entered on study centrally at the VICC Coordinating Center. All sites should email the Coordinating Center at [contact] to verify treatment availability prior to enrollment.

All patients MUST be enrolled with the VICC prior to the start of protocol treatment. Enrollment can only be conducted during the business hours of 8AM – 5PM Monday through Friday.

- 1) All sites should email the [VICC Coordinating Center [contact]](mailto:[contact]) to notify of upcoming enrollment and slot availability. The following information should be included in your email:
 - Study Number
 - Patient Initials
 - Anticipated Consent Date
 - Anticipated Start Date

- 2) To enroll, email the following documents to the Coordinating Center for eligibility review and patient enrollment ([VICC Coordinating Center [contact]](mailto:[contact])):
 - Copy of the patient's signed and dated Informed Consent, including documentation of the consent process.
 - HIPAA authorization form (if separate from the main consent form)
 - VICC Patient Enrollment Form
 - Copies of supporting source documentation including any laboratory, imaging and pathology reports or EMR access
 - Completed Eligibility Checklist. **To be eligible for the study, the participant must meet each inclusion criterion listed in the eligibility checklist.**

Note: VICC Coordinating Center requests that sites **send eligibility documents 24-48 hours prior to planned enrollment**. Same day treatment enrollments will only be accepted with prior notice and discussion with the Coordinating Center. Please email the Coordinating Center if enrollment is needed sooner.

Once enrollment confirmation from Coordinating Center is received, proceed with protocol procedures.

Please contact the assigned Study Contact with any questions regarding this process. You can also reach out to your assigned CRA once the study is activated.

The VICC Coordinating Center will assign subject IDs to all patients in screening. Only patients deemed eligible will be registered to investigational treatment. Sequence numbers will not be re-used if a patient screen fails unless the same patient re-screens at a later point. Following enrollment confirmation by the coordinating center, eligible participants should begin study treatment consistent with the protocol no later than 21 days after the baseline/screening MRI.

Issues that would cause treatment delays should be discussed with the Protocol Chair. If a participant does not receive protocol therapy following enrollment within allowed time period, the participant will become ineligible and will be removed from the study. Such patients will have to undergo re-screening in order to participate in the study. Any requests for eligibility exceptions and/or deviations must be approved in writing by the Protocol Chair and the VICC DSMC.

As is generally accepted, standard of care procedures performed prior to consent, but within the protocol defined screening window for each assessment, can be used for study purposes. All research-only procedures must be performed after the patient consents.

6. Clinical Investigation-related Procedures

a) NovoTTF-200A System Treatment

[figure not shown]
- 1. Treatment planning: Transducer array layout will be determined by the investigator or Novocure using the NovoTALTM software supplied by Novocure. NovoTAL can be used for multiple tumors as is often the case with GBM (the approved indication for the Optune System). There is no difference in the field mapping algorithm based on histology of the tumor or frequency of the TTFields.

- 2. Patient training: Patients will be trained in the use of the device by the investigator, a designated health care provider (e.g. nurse) or Device Support Specialist (DSS) trained by Novocure.
- 3. Treatment initiation: NovoTTF-200A will be initiated by the investigator within 4 weeks of completion of chemotherapy. All patients will be required to shave their heads to initiate array placement and TTFields. Array placement will be performed based on the Transducer Array Layout

map calculated during treatment planning.

4. Treatment duration: Treatment with the device will be continuous with breaks allowed for personal needs (e.g. showering, array exchange) and for MRI imaging assessments. Patients must use the device for at least 18 hours a day on average. Treatment will be continued until intracranial failure (as defined in section 9(a) of the protocol), death, or unacceptable side effects to patient. Patients must use the device for a minimum of 4 weeks from treatment initiation. A treatment break of 3 days per month in NovoTTF-200A is allowed. However, the patient should use the device for at least 18 hours a day on average as stated above.
5. The NovoTTF-200A System will be programmed by Novocure to deliver 200 kHz TTFIELDS in two sequential, perpendicular field directions at a maximal intensity of 707mA RMS. There will be no adjustments made to the device by investigators or patients/caregivers.
6. Transducer Array replacement: Patients will replace the Transducer Arrays twice to three times per week independently or with the help of a caregiver. At each array replacement the patient's scalp will be re-shaved and skin treated according to the guidelines set out below.

7. Compliance assessment: The device will be inspected either by the investigator or by a

Novocure representative on a monthly basis to assess patient compliance with therapy.

8. The following skin care guidelines should be closely adhered to:
 1. If the skin beneath the Transducer Arrays is inflamed, a high potency topical steroid (e.g. clobetasol) should be prescribed to the patient. The patient or caregiver should apply the ointment after removing the arrays and cleaning the scalp with baby oil and medical alcohol. The ointment should be left on the scalp for at least 30 minutes prior to washing the skin with a mild shampoo and applying a new set of arrays.
 2. At each array replacement, the new set of arrays should be shifted by approximately 2 cm compared to the previous layout so that the array discs are placed between the areas of skin irritation. At the next array replacement the arrays should be shifted back to their original location.
 3. If the dermis is breached (skin erosions, ulcers, open sores, punctate lesions, etc.) an antibiotic ointment (e.g. mupiricin) should be prescribed and used in place of the steroid ointment. Any evidence of infection should result in bacterial cultures being taken. There will be no “dose” adjustments to the device for adverse events. Compliance data will be reviewed biweekly. Review of the compliance data and the reasons for breaks in treatment for longer than 24 hours will be documented in the eCRFs. The maximum duration of treatment break allowed for adverse events related to TTFields is 3 weeks.

b) Systemic Therapy

Patients should have completed 4 to 6 cycles of first-line chemotherapy prior to the start of study treatment. If patients develop progressive extracranial disease during study, then the patient may receive systemic therapy at the discretion of the treating physician while on NovoTTF-200A. Systemic therapy utilized will be documented in the CRFs.

c) Chest irradiation

Patients may receive chest irradiation at the discretion of the treating physician while on NovoTTF-200A. Radiation therapy utilized will be documented in the CRFs.

c) Salvage Therapy

Following intracranial failure, patients may be offered salvage therapy based on local practice at each site including, but not limited to:

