1. OVERALL SYNOPSIS OF THE CLINICAL INVESTIGATION

Title:	A Multi-Institutional Pilot Study of Prophylactic Cranial Tumor-Treating Fields for Patients with Extensive-stage Small Cell Lung Cancer
Device:	NovoTTF-200A System (200kHz output frequency)
Study Objectives:	To test the feasibility and compliance of TTF therapy to the brain in patients with extensive-stage small cell lung cancer with no evidence of brain metastasis. Secondary endpoints include overall survival, development of brain metastases, neurocognitive function, and QOL outcomes.
Study Design:	Prospective open label pilot study
Study Hypothesis:	The hypothesis of this study is that NovoTTF-200A will reduce the risk of developing brain metastases for ES-SCLC patients.
Sample Size:	25 patients treated with NovoTTF-200A
Study Population:	Patients with histologically proven small cell lung cancer who have undergone at least four cycles of first-line chemotherapy with a partial or complete response, above 22 years of age, no evidence of intracranial metastasis.
Primary Endpoint:	Feasibility, as measured by tolerability of TTFs (% patients continuing TTF therapy until intracranial tumor progression, discontinuation due to DLT, or 6 months).
Secondary Endpoints:	
 • Time to intracranial failure • Overall survival • Rates of intracranial failure at 2, 4, 6, 8, 10, 12 months after NovoTTF-200A • Intracranial failure free survival • Rate of decline in HVLt-R free recall, delayed recall and delayed recognition, COWAT and TMT Parts A and B at 2, 4, 6, 8, 10, 12 months after NovoTTF-200A • Time to neurocognitive failure • Neurocognitive failure-free survival • Quality of Life using the EORTC QLQ C30 with BN20 addendum • Adverse events, severity and frequency based on CTCAE V5.0
Sponsor:	[name], Vanderbilt University Medical Center

STUDY SCHEMA

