9. STATISTICAL CONSIDERATIONS

a) Study Endpoints

The primary endpoint is feasibility, measured as percentage of patients continuing TTF therapy until

intracranial tumor progression, discontinuation due to DLT, or 6 months. Death prior to evidence of intracranial failure is treated as a competing risk and the patient is censored at time of death. Death will not be considered as an event and patients who have not had intracranial failure will be censored at the time of death.

Secondary endpoints include:

- Time to intracranial failure, as measured from date of starting NovoTTF-200A to intracranial failure as a first event. Death prior to evidence of intracranial failure is treated as a competing risk and will be censored on the time to intracranial failure curves.
 - Intracranial Failure will be diagnosed based on ONE of the following criteria:
 - New lesion seen on two consecutive axial slices
 - New lesion seen on at least one slice in two separate planes
 - MRI used to diagnose intracranial failure must meet requirements mentioned in inclusion criteria, specifically, the MRI must be a high resolution, isovolumetric T1-weighted post-gadolinium MRI of the brain using a 3T MR scanner. Additional parameters include:
 - FOV: 256 mm x 256 mm
 - Matrix: 256x256
 - Slice thickness: 1 mm
 - Full brain Coverage
 - A lesion is designated “Undetermined” as long as it does not comply with the definition of intracranial failure above. If on a subsequent scan or on an additional imaging modality it is deemed as intracranial failure according to the criteria above, the date of intracranial failure diagnosis will be documented as the first time a new lesion was evident on a scan (i.e., backdated).
- Overall survival, defined from the date of starting NovoTTF-200A to death due to any causes, or censored at the date of last follow-up.
- Rate of intracranial failure at 2, 4, 6, 8, 10, 12 month after starting NovoTTF-200A
- Intracranial failure free survival, defined from the date of starting NovoTTF-200A to the first intracranial failure or death (whichever occurs first) or, otherwise, censored at the last MRI imaging assessment date on which the patient was reported alive without intracranial failure.
- Rate of decline in cognitive function as measured by HVLT-R free recall, delayed recall, and delayed recognition; COWAT; and TMT Parts A and B at 2, 4, 6, 8, 10, 12 months follow-up.

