NCCTG N0574, NCCTG N0577, RTOG 0825, ECOG E3F05, NCCTG N0874/ABTC 09-0, and N107C. Assessments will be conducted every 8 weeks for the first year or until intracranial failure, whichever occurs first. The HVLt-R test has been used and validated in multiple prior phase III trials of patients with brain metastases [9, 21]. HVLt-R incorporates 6 different forms, helping to mitigate practice effects of repeated administrations. Each form includes 12 nouns (targets) with 4 words drawn from 3 semantic categories, which differ across the 6 forms. The test involves memorizing a list of 12 targets for 3 consecutive trials (immediate recall), recalling the 12 targets after a 20-minute delay (delayed recall), and identifying the 12 targets from a list of semantically related or unrelated items (delayed recognition). In COWAT [Johnson SC et al, *Clin Neuropsychol.* 2012; 26(7):1230-41, Johnson DR et al, *Neuro Oncol.* 2012;14(6):808-16], the patient produces as many words as possible in 1 minute for a specific letter and the test assesses language and executive/frontal skills. The test is widely used and is part of the Halstead-Reitan Neuropsychological Battery. Impairment in the understanding of language or the motor expression of language will impair the results in this trial. Since such functions are affected by brain-directed therapies such as WBRT, the test could be sensitive to the experimental treatment effects on those functions. TMT [Bowie CR and Harvery PD, *Nat Protoc.* 2006; 1(5):2277-81] is a measure of visuospatial scanning, attention, sequencing and cognitive processing speed (Part A) and executive function (Part B). Those neurocognitive functions could be affected both by brain metastasis and by therapies directed to the brain, and will therefore be used in the trial. Patients must “connect the dots” either in a numbered sequence or alternating letters and numbers.

b) Sample Size Determination: Because the primary endpoint is feasibility, the proposed sample size is not driven by statistical hypotheses. Rather, we propose the sample size of 25 so that we will have precise enough information for planning the next phase of treatment development. The following table summarizes the point estimate and 95% confidence interval when n=25.

# patients continuing therapy	10	15	18	20
Point estimate	40%	60%	72%	80%
95% confidence interval	23% - 59%	41% - 77%	52% - 86%	61% - 91%

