c) Statistical Analysis – Primary Endpoint: Since this is a feasibility study, we will not attempt a strict control of multiplicity in analyses of the primary and secondary endpoints. Proportion of patients continuing TTF will be estimated using Wilson’s method and a one-sided 95% confidence interval will be reported. We will also summarize this measure for those who had PR and CR separately.

d) Statistical Analysis – Secondary Endpoints

Secondary endpoints for statistical testing: Time to intracranial failure with death as a competing risk will be estimated using cumulative incidence function (CIF) and reported with a one-sided 95% confidence interval. Rate of intracranial failure at a given time will be estimated using the CIF. Overall survival will be estimated using the Kaplan-Meier method. Other time-to-events data (with or without competing risks) will be analyzed similarly. Quality of life will be treated as a continuous endpoint; its mean will be estimated and reported with a 95% confidence interval. Toxicity (CTCAE 0-4) will be tabulated.

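### As worded, the primary tolerability rate counts a toxicity stop as a qualifying end, leaves DLT undefined, and gives on-therapy deaths no place in a simple proportion

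*Combined protocol and SAP*

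**What the plan says.** The same three ends of therapy appear in four places. Section 6.1(b) gives the primary outcome as the "percentage of patients continuing TTF therapy until intracranial tumor progression, discontinuation due to DLT, or continuation of therapy for at least 6 months". The synopsis and the primary objective in section 5(a) use the same list, and section 9(a) repeats it as "intracranial tumor progression, discontinuation due to DLT, or 6 months". The synopsis and section 6.1(b) say the measure reflects tolerability; the synopsis and section 5(a) also name compliance as an aim. Section 3(e) expects 75% or more of patients to tolerate at least six months of treatment.

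DLT is expanded in the list of abbreviations and defined nowhere. Three other rules bear on toxicity stops, and none mentions DLT:

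- Section 6.4 allows removal for intolerable device-attributable events and requires immediate cessation for a life-threatening serious event definitely related to the device.
- The treatment-duration item in section 6.6(a) ends therapy for side effects unacceptable to the patient.
- The skin-care text in section 6.6(a) caps breaks for related adverse events at 3 weeks.

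Directly under the primary endpoint, section 9(a) treats death before intracranial failure as a competing risk and adds: "Death will not be considered as an event and patients who have not had intracranial failure will be censored at the time of death". Section 9(c) then says: "Proportion of patients continuing TTF will be estimated using" Wilson's method, with a one-sided 95% interval. The precision table in section 9(b) is indexed by the number of "patients continuing therapy".

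**The concern.** The three ends are grammatically parallel. If reaching progression or six months satisfies the definition, so does reaching a DLT stop, and no section classes that stop as a failure. A tolerability rate that toxicity stops cannot reduce does not measure what it is named for.

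Because DLT is undefined and unconnected to the removal rules, the same device problem could count as a success if recorded as a DLT and as a failure if recorded as a patient request.

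The death rule is a separate gap. A binomial proportion needs every patient in the numerator, in the denominator only, or out of both. Censoring assigns none of these.

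Section 9(b) justifies 25 patients on the ground that "we will have precise enough information for planning the next phase of treatment development", and section 3(e) makes tolerability, with safety, a condition for considering phase 2. Two analysts who follow the text could report different primary rates from the same data. In an open-label single-arm study, a choice made after outcomes are seen would be open to bias.

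**Working it through.** **Inputs.** From the documents: n = 25 and the interval table (section 9(b)); Wilson's method, one-sided 95% (section 9(c)); the 75% expectation (section 3(e)); median survivals of 6.7 and 5.4 months in the European trial and 10.1 and 15.1 months in the Japanese trial, each with versus without cranial irradiation (section 3(a)). Assumed, because the documents give no figure: DLT-stop rates of 2% and 5%, 1 to 3 on-therapy deaths, and exponential survival. The nearest toxicity figures, in section 16.1(a), are no device-attributed serious events in recurrent glioblastoma and 2% grade 3 skin reactions in EF-14. They are an imperfect proxy and favour the low end.

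**Step 1: reproduce the plan's table.** The Wilson limits are [p + z²/2n ± z√(p(1−p)/n + z²/4n²)] / (1 + z²/n). For 18/25 with z = 1.96, the centre is (0.72 + 0.0768)/1.1537 = 0.691 and the half-width 0.166, so the interval is 52.4% to 85.7%. The other columns give 23.4–59.3% (10/25), 40.7–76.6% (15/25) and 60.9–91.1% (20/25). All match the table after rounding, so the table is two-sided Wilson.

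**Step 2: effect of the DLT wording.** One patient is 100/25 = 4 points. Suppose 18/25 qualify when DLT stops are failures.

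| DLT stops | Literal reading | Two-sided 95% | One-sided lower bound |
|---|---|---|---|
| 0 | 18/25 = 72% | 52–86% | 56% |
| 1 | 19/25 = 76% | 57–89% | 60% |
| 2 | 20/25 = 80% | 61–91% | 64% |

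Expected stops are 25 × 0.02 = 0.5 and 25 × 0.05 = 1.25, so the mean shift is 0.5 × 4 = 2 points or 1.25 × 4 = 5 points. The plan's own interval at 72% is 86 − 52 = 34 points wide.

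**Step 3: effect of the death wording.** Take 18 qualifying patients, no DLT stops, and deaths on therapy before 6 months without intracranial failure.

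| Deaths | Success | Excluded | Failure |
|---|---|---|---|
| 1 | 19/25 = 76% | 18/24 = 75% | 18/25 = 72% |
| 3 | 21/25 = 84% | 18/22 = 82% | 18/25 = 72% |

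**Step 4: how many deaths could be affected.** Under exponential survival, the probability of death by 6 months is 1 − 0.5^(6/median).

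- Japanese trial (MRI screening required): 15.1 months gives 0.241, or 6.0 of 25; 10.1 months gives 0.338, or 8.4 of 25.
- European trial (no MRI screening): 6.7 months gives 0.462, or 11.6 of 25; 5.4 months gives 0.537, or 13.4 of 25.

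This trial excludes patients with brain metastases on MRI, so the Japanese trial is the closer guide. These are deaths from any cause. Some would follow intracranial failure or an earlier stop, so 6 to 8 is an upper limit for the unclassified deaths, not an estimate of them.

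**The case against.** The strongest defence is that the endpoint measures adherence. The synopsis and section 5(a) name compliance as an aim, and continuing until a protocol-permitted stop is a coherent adherence measure; intracranial progression is already treated that way. This shows that the wording could be deliberate. It does not rescue the endpoint as labelled, because the synopsis and section 6.1(b) say feasibility is measured by tolerability.

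Second, the count of patients continuing therapy in sections 9(b) and 9(c) could imply that a DLT stop is a failure. It could, but it does not settle the matter.

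Third, the DLT effect is small beside the sampling error, and toxicity is tabulated separately under section 9(d). Both stand. DLT stops would be visible in the safety tables, though not in the feasibility rate.

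Fourth, the death sentences closely match those for time to intracranial failure and may have been carried over. That may explain them, but they stand under the primary endpoint.

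A reader might infer that the plan sets out to count toxicity as success, or to hide it. The documents support only an ambiguity that the literal wording resolves badly. A reader might also infer that every early death is unclassified. That goes too far: a patient who stopped earlier for another reason can be classed by that stop, and only deaths while still on therapy are left without a place.

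**Conclusion.** The point holds and should be settled before outcomes are reviewed. As written, toxicity stops cannot lower the tolerability rate, the term that would identify them is undefined, and on-therapy deaths cannot be placed in the planned analysis.

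The DLT part is probably minor in size. The death part may matter more: up to 12 points (84% against 72%) with three such deaths. Both sizes rest on assumed counts and rates. The gaps in definition do not.

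Two stronger conclusions are tempting and not supported. One is that the wording could reverse a go/no-go decision at 75%: section 3(e) states an expectation, and the protocol sets no decision threshold. The other is that about half the patients would fall into the gap: the 12 to 13 deaths behind that come from patients not screened by MRI and include all causes.

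**What to change.** These changes apply to the endpoint analysis only, alter no stopping rule, and should be fixed before outcomes are reviewed.

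1. Classify each patient by the first reason therapy ended before 6 months, with all treated patients in the denominator. Because the measure is tolerability, count a permanent stop for a device-related adverse event as a failure, and replace the DLT clause accordingly in the synopsis and sections 5(a), 6.1(b) and 9(a). If the sponsor intends an adherence measure, label it so and report beside it the rate with these stops as failures.
2. Reconcile the endpoint term with section 6.4 and with the duration and break provisions of section 6.6(a), so that one event cannot be classed two ways. Which events qualify is for the sponsor to decide.
3. Delete the two censoring sentences attached to the primary endpoint in section 9(a); keep censoring or competing-risk handling for the time-to-event endpoints. State one primary classification for deaths while still on therapy before 6 months without intracranial failure, and give the rate under the alternative classification as a sensitivity analysis. Deaths after an earlier stop take the class of that stop.
4. State whether the 75% in section 3(e) refers to this endpoint or to strict six-month use, and report stops by reason beside the primary proportion.

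The cost is a protocol amendment, which section 11 sends to the IRBs and FDA if it significantly affects scientific quality, and the reported rate may be lower. Section 6.6(a) has reasons for breaks over 24 hours recorded in the eCRF; the sponsor should confirm that the reason for a permanent stop is captured too.
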